This project presents an innovative proposal, addressing a BCG vaccine with known efficacy against severe TB in childhood and reliable for the use of adjuvant therapy in patients with malignant bladder neoplasia.

BCG is an easily accessible vaccine, widely used by SUS in newborn children, thus facilitating its incorporation into a new preventive proposal for COVID-19. In addition, the selection of health professionals will be based on diagnostic screening and confirmatory tests of COVID-19.

It is intended to analyze the role of BCG in the prevention of infection and also in the occurrence of severe forms of COVID-19 in addition to evaluating the immune response mediated by this vaccine in voluntary health professionals.

GOALS:

In the period of 6 months, to analyze the effect of BCG as a protective factor for COVID-19 in research volunteers, aiming at greater efficiency in the prevention of subjects at high risk of infection and evolution to severe forms of the disease, as well as to evaluate the specific and non-specific immune responses to SARS-CoV-2 in vaccinated and unvaccinated volunteers who evolved with COVID-19 or not.

Primary Objectives:

1. Assess the impact of BCG vaccine administration on the cumulative incidence of SARS-CoV-2 infection
2. Assess the impact of BCG vaccine administration on the cumulative incidence of severe forms of COVID-19
3. Evaluate the bcg vaccine-mediated immune response in volunteers

Secondary Objectives:

In groups receiving BCG or placebo, infected and not infected with SARS-CoV-2:

- Epidemiological:

1. Estimate whether BCG vaccination compared to placebo prolongs the time to the first respiratory disease proven by SARS-CoV-2;
2. Estimate whether BCG vaccination compared with placebo reduces the proportion of symptoms associated with COVID-19 (fever or at least one sign/symptom of respiratory disease);
3. Estimate whether BCG vaccination compared to placebo reduces absenteeism (missing days) in volunteers who are health professionals;
4. Analyze the safety of BCG vaccination in adult volunteers;

- Laboratories:

5. Describe the inflammatory profile by dosing neutrophils, platelets, cit-H3, alpha 1 antitrypsin (α 1AT), galectin-2, ferritin, transferrin-R, glycated hemoglobin (HbA1c),

C-reactive protein (CRP), D-dummer, LDH, albumin and hemosedimentation velocity (ESR);

6. Describe the profile of inflammatory cytokines identified in the BCG and placebo groups, comparing to the protective events to SARS-CoV-2;

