According to CNS Resolution No. 441 of 2011 (Art. 1) and Ordinance MS No. 2,201 of 2011 (Art. 3), any organized collection of human biological material collected for scientific research purposes, including samples intended for routine examinations in a clinical trial (e.g., blood count and renal function) are considered as constituents of a biorepository or biobank. The biological material will be used as provided for in the research protocol, with no further future analyses different from those foreseen. If there is a proposal for future use of the stored samples, approval in the CEP/CONEP system will be required and a new protocol and TCLE will be submitted so that each participant can choose whether or not to allow the use of the samples for future studies.

Statistical Analysis Plan:

The primary efficacy analysis will compare the cumulative incidence of SARS-CoV-2 infection and the cumulative incidence of severe forms of COVID-19.

These analyses will occur when the last enrolled research subject has completed 30 days and 6 months of preventive treatment and will be performed using the results of COVID-19 diagnostic tests, as well as the data available in participating hospitals and national electronic notification systems of COVID-19. A modified treatment intention analysis (MITT) and protocol (PP) will be performed. The safety and tolerability analysis will consist of all patients who have been randomized and received a dose of the vaccine or placebo. Based on serum immune response concentrations, we will calculate certain immunoinflammatory variables related to the use of BCG versus placebo among subjects infected and not infected by COVID-19 among the categories with COVID-19 vaccine (Coronavac® or Covishield®) and without covid-19 vaccine.

The intervention and control groups will be compared at the time of inclusion in the study in relation to sociodemographic, clinical, radiological and biochemical imaging variables, in order to evaluate the adequacy of the randomization process. Multivariate

analyses using logistic regression or Poisson models with robust variance will be used to evaluate the effect of BCG vaccine on primary and secondary outcomes. Associations will be expressed in the form of risk ratios and respective 95% confidence intervals. Data imputation may be required and the *random forest system* will be used. Statistical software R, version 10.0.

Sample size:

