It is estimated that it will take 376 individuals in each of the comparison groups to ensure a statistical power of 80% and a type I error of 5%, considering an incidence of SARS-CoV-2 infection of 20% in BCG vaccinated, 30% in unvaccinated, 15% in covid-19 vaccinated. It is expected a reduction in the joint effect of BCG with the COVID-19 vaccine between 10% and 15% and that the percentage of people vaccinated with BCG in the cohort is 50% and the percentage of people vaccinated for Covid-19 in the cohort is 80%.

We will also use for the two outcomes (below) the sequential design the groups are followed up until there is a group with clear benefits or that both groups do not present difference. This design is used when the results need to be known very quickly. If there is a large difference between the treatments, then this study will be performed in a shorter time when compared to the parallel trial. The main ethical advantage is that if one treatment shows a superiority over the other, the study can already be stopped. However, the interim analyses will be previously planned, in such a way that the calculation of sample size allows the multiplicity of the tests. The meaning of p-values in sequential analyses also changes, because when using sequential analyses, more than one analysis is performed, and the typical definition of a p-value as data "at least as extreme" as observed needs to be reset. One solution is to sort the p-values of a series of sequential tests based on the downtime and at what time the test statistic was in a certain appearance, known as ordering.

OUTCOMES:

Primary Outcome

1. Compare the cumulative incidence of SARS-CoV-2 infection

It is estimated that it will take 376 individuals in each of the comparison groups to ensure a statistical power of 80% for the detection of a difference in effects of 10%, considering that the control group will have an accumulated incidence of SARS-CoV-2 infection of 30% after 6 months of follow-up, for a type I error of 5%.

2. Compare the cumulative incidence of severe forms of COVID-19

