We will also use for the two outcomes the sequential design the groups are followed up until there is a group with clear benefits or that both groups do not present difference. This design is used when the results need to be known very quickly. If there is a large difference between the treatments, then this study will be performed in a shorter time when compared to the parallel trial. The main ethical advantage is that if one treatment shows a superiority over the other, the study can already be stopped. However, the

interim analyses will be previously planned, in such a way that the calculation of sample size allows the multiplicity of the tests. The meaning of p-values in sequential analyses also changes, because when using sequential analyses, more than one analysis is performed, and the typical definition of a p-value as data "at least as extreme" as observed needs to be reset. One solution is to sort the p-values of a series of sequential tests based on the downtime and at what time the test statistic was in a certain appearance, known as ordering.

3. Assess the BCG vaccine-mediated immune response in healthcare professionals

SARS-CoV2 infection is estimated to occur in approximately 20% of health professionals vaccinated by BCG (experimental group), in 30% of health professionals not vaccinated by BCG (placebo group) and not vaccinated for COVID-19 and in 15% in COVID-19 vaccinated without BCG vaccine. A reduction of 10% to 15% of the joint effect of bcg vaccine with Covid-19 vaccine is expected.

In this scenario, with the bearing of 376 health professionals in each arm, if we assume that the percentage of covid-19 vaccinated is 80% and equal in each arm, SARS-CoV2 infection is expected to be detected in 15 professionals vaccinated only with BCG, in 23 professionals not vaccinated with BCG and COVID-19 vaccine, 45 professionals vaccinated for COVID-19 without bcg vaccine and 38 professionals vaccinated for COVID-19 and BCG. For each subgroup (vaccinated and not vaccinated with BCG) it will be possible to identify the predictive biomarkers of infection by comparing infected professionals with those who were not infected with SARS-CoV2.

INTERIM ANALYSIS PLAN:

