Regarding the effect of BCG vaccine administration on the cumulative incidence of SARS-CoV-2 infection or on severe forms of COVID-19, a single intermediate analysis will be performed when the number of volunteers included has reached half of the total sample scheduled to verify whether the evidence would already be conclusive and would allow the study to be interrupted. For type I error protection, intermediate analysis will use a Z value of 2.78 (Chow & Liu, 2004).

The analyses that will be performed in the intermediate analysis will be restricted to the following outcomes: accumulated incidence of SARS-CoV-2 infection, cumulative incidence of severe forms of COVID-19 and proportion of serious adverse events.

The following rules will be used to indicate early completion of the study after intermediate analysis:

- Significant difference in the effect of BCG judged by comparing the proportions of patients who develop SARS-CoV-2 infection or severe forms of COVID-19 in each arm of the study;

- If the effect of BCG is similar between groups and there is a significant difference in the cumulative proportion of serious adverse events;

The results will be evaluated by the Data and Safety Monitoring Committee, which will express the need to continue the study, based on the vaccine's performance in terms of the incidences of SARS-CoV-2 infection or severe forms of COVID-19 and adverse events.

Independent Data Monitoring and Security Committee:

The Data and Safety Monitoring Committee (CMDS) will be composed of three members not linked to participating institutions, in accordance with the Operational Guidelines for the Establishment and Functioning of Data Monitoring and Safety Committees of the Ministry of Health (2008).

This committee will be responsible for reviewing the protocol and progress of the study in all centers, with real-time meetings by videoconference, as detailed below, and will consist of:

[name] - Physician - Professor, Faculty of Medicine, Federal University of Rio Grande do Sul

[name] - Statistician - Institute of Collective Health Studies of the Federal University of Rio de Janeiro

[name] - Physician - Professor, Faculty of Medicine, Federal University of Minas Gerais

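### Infection and severe COVID-19 are both primary with no final success rule; if either one suffices, the chance of a false positive is about 5% to 10.5%, not a fixed 5%

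*Combined protocol and SAP*

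**What the plan says.** The primary efficacy comparison in the Statistical Analysis Plan covers two outcomes: "The primary efficacy analysis will compare the cumulative incidence of SARS-CoV-2 infection and the cumulative incidence of severe forms of COVID-19". The Primary Objectives list them separately; the second reads "Assess the impact of BCG vaccine administration on the cumulative incidence of severe forms of COVID-19". The Primary Outcome list repeats both and adds immune response as a third item. It also states: "We will also use for the two outcomes the sequential design".

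The type I error appears only with infection incidence, in Sample size and under the first primary outcome: "accumulated incidence of SARS-CoV-2 infection of 30% after 6 months of follow-up, for a type I error of 5" per cent. Severe COVID-19 has no expected rate, effect size, power or error rate.

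The Interim Analysis Plan schedules one look "when the number of volunteers included has reached half of the total sample" planned, which is 376 of 752. The CMDS activity plan places it after 500 participants. On the boundary, the plan says the "intermediate analysis will use a Z value of 2.78"; no final critical value is given. The first early-completion rule compares the proportions of "patients who develop SARS-CoV-2 infection or severe forms of COVID-19 in each arm of the study".

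The Statistical Analysis Plan schedules the primary analyses both 30 days and 6 months after the last enrolment and does not say which decides. On reporting: "Associations will be expressed in the form of risk ratios and respective 95% confidence intervals".

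**The concern.** With two primary outcomes and no rule joining them, the plan does not define a positive trial. A result significant on severe COVID-19 but not on infection could be reported as success or as failure, and both would be consistent with the text. If the rule is chosen after unblinding, it can be fitted to the result. The stated 5% describes the infection test, where it nearly holds, and not the trial's overall claim. The monitoring committee has the same difficulty at the interim, where either outcome can signal early completion.

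**Working it through.** **Inputs from the documents.** 376 per arm, 1:1; infection 30% v 20%; 80% power; 5% type I error; interim Z = 2.78; 95% intervals; recruitment from 30/10/2020 to 31/12/2021 (14 months); 6 months of follow-up.

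**Assumed, because the documents do not say.** Two-sided tests; final value 1.96 (implied by the 95% intervals); the correlation of the two outcomes; the share of infections that are severe. The per-protocol analysis and the immune-response objective are not counted.

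**1. The plan's own figure.** n = [1.96·√(2·0.25·0.75) + 0.842·√(0.21 + 0.16)]² / 0.10² = 294 per arm, or 313 with continuity correction. The stated 376 is not reproduced; with 376 per arm the power is 88.8%. Unstated adjustments come close: 313 × 1.20 = 376, and alpha 0.025 with continuity correction gives 375.

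**2. Two outcomes, no interim look.** 1 − 0.95² = 9.75% if independent, 5% if perfectly correlated, at most 10%.

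**3. Interim information t.** With uniform recruitment, half are included at month 7. They have accrued 1×6 + 18 = 24 person-months per unit of the monthly recruitment rate, out of 14×6 = 84, so t = 0.286. An upper bound is 500/752 = 0.665.

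**4. Adding the interim, normal theory.** Stage statistics have correlation √t; rejection means |Z| > 2.78 at the interim or > 1.96 at the end. P(|Z| > 2.78) = 0.0054. The either-outcome rows are simulated, 2 million trials each.

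| | t = 0.286 | t = 0.50 | t = 0.665 |
|---|---|---|---|
| Infection alone | 5.35% | 5.21% | 5.10% |
| Either, correlation 0 | 10.4% | 10.2% | 9.9% |
| Either, correlation 0.5 | 9.7% | 9.5% | 9.2% |
| Either, correlation 0.8 | 8.4% | 8.1% | 8.0% |

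The missing final value accounts for only 0.1 to 0.35 points (infection row minus 5%).

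**5. Simulated counts.** Severe cases are nested in infections; 400,000 trials; t = 0.5; a zero cell counts as not significant for Wald. The expected counts under the third primary outcome give (15 + 23 + 45 + 38)/752 = 121/752 = 16.1% infected. Either outcome suffices:

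| Share of infections severe (assumed) | 2% | 5% | 10% | 20% | 30% |
|---|---|---|---|---|---|
| Expected severe cases, 16.1% infected | 2.4 | 6.1 | 12.1 | 24.2 | 36.3 |
| Wald log risk ratio, 16.1% | 5.0% | 5.4% | 7.3% | 8.6% | 8.7% |
| Pooled z, 16.1% | 7.2% | 9.6% | 9.1% | 9.6% | 9.2% |
| Wald log risk ratio, 30% | 5.2% | 7.2% | 8.8% | 9.1% | 9.1% |
| Pooled z, 30% | 9.4% | 9.3% | 9.9% | 9.6% | 9.5% |

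**6. Either at the interim, both at the end.** 1.3% to 3.0% by normal theory; 0.3% to 1.8% by counts.

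**7. If the 30-day analysis is also a test at 1.96.** One month after the last enrolment the information is (9×6 + 17.5)/84 = 71.5/84 = 0.85. Infection alone becomes 6.8% to 7.1%. Either outcome becomes about 12.2% to 13.7% at correlation 0 to 0.5, and about 10.5% to 11.0% at 0.8.

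**8. Power on infection.** Φ{[|p₁ − p₂| − c·√(2p̄q̄/376)] / √[(p₁q₁ + p₂q₂)/376]}. The plan's expected counts by arm are 23 + 45 = 68 (placebo) and 15 + 38 = 53 (BCG).

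| Final critical value c | 30% v 20% | 68/376 v 53/376 |
|---|---|---|
| 1.96 | 88.8% | 32% |
| 1.991 to 1.969 (5% test) | 88.2% to 88.6% | 31% to 32% |
| 2.045 to 2.020 (severe-only signal kept) | 87.1% to 87.6% | 29% to 30% |
| 2.312 to 2.272 (2.5% test) | 80.5% to 81.6% | 20% to 22% |

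**The case against.** The strongest case against is that the inflation is conditional. The *or* in the Interim Analysis Plan governs a recommendation to stop; it is not a claim of success. If the plan intends both outcomes to succeed at the end, there is no inflation. That stands, and it is why every figure above is tied to a stated rule.

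The planned models, logistic or robust Poisson regression with risk ratios, are closest to the Wald results. On that basis the rate is about 5% to 9%, and with very few severe cases there is hardly any inflation. That also stands. Values near 10% come from pooled z or normal theory; comparing proportions is mentioned only for the interim.

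Other defences do not hold. The multiplicity and ordering text in Sample size and under Primary Outcome concerns repeated looks, as does 2.78. The numbering of the outcomes is a list; no text makes it a testing sequence. The closeness of 376 to the 375 needed at alpha 0.025 could suggest a hidden split, but the text states 5% and a 20% addition to 313 fits as well.

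A reader might infer that the trial's type I error simply is 10%, or that either outcome is the declared success criterion. The documents support neither: they leave the final rule open.

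**Conclusion.** The gap is real and should be closed before unblinding. Two outcomes are primary, and no final success rule, order or alpha split is given. If either is enough, the chance of a false positive primary result is about 8% to 10.5% by normal theory (correlation 0 to 0.8), about 5% to 9% with a Wald risk ratio and about 7% to 10% with pooled z. If both are needed at the end, it is 3% or less. Infection alone stays at 5.1% to 5.35%.

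All of this assumes that the 30-day analysis is not a test. If it is, infection alone is about 7% and either outcome about 10.5% to 14%. The rate of severe disease, the correlation and the final critical value are not in the documents, so the range cannot be narrowed. The missing final value and the two interim timings are lesser matters.

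**What to change.** Before unblinding, amend the SAP wording and notify the monitoring committee:

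1. State that the 6-month analysis is decisive and the 30-day analysis descriptive.
2. Test infection first, and severe COVID-19 only if infection is significant.
3. Reconcile the interim timing between the Interim Analysis Plan (half of the sample, 376) and the CMDS activity plan (500 participants).
4. Set the final critical value from the actual information fraction. After 2.78 at information 0.29 / 0.50 / 0.665 it is 1.991 / 1.979 / 1.969. If the severe-only efficacy signal at the interim is kept, it adds 0.2 to 0.6 points of error, and the final value for infection becomes 2.045 / 2.031 / 2.020.

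**Cost.** No added participants. Severe COVID-19 loses its stand-alone claim and, if the order also applies at the interim, its stand-alone stopping signal. Power on infection is about 87% to 88% for 30% v 20%, but only about 29% to 31% on the plan's own expected counts with 80% COVID-19 vaccinated. That low figure is not caused by the change, since it is about 32% at 1.96.

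**Alternative.** Keep both primary at 2.5% each, with final values 2.312 / 2.291 / 2.272. This costs more: power on infection falls to 80% to 82% for 30% v 20%, and to about 21% on the expected counts.

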Health professionals from other institutions besides those participating in the study may participate in the research. In this case, they will contact the participating centers, through telephone contact or email, informing their interest. All follow-up of these participants will be carried out by the center in which the subject was recruited.

The first evaluation (*Screening* or recruitment) of the study can be initiated in person or through telephone contact, email or electronic media. If the eligibility criteria are met, the individual will be invited to attend the study center for the signing of the Informed Consent and collection of exams that will confirm his or her eligibility or not.

Over four other face-to-face visits [M0 or inclusion, M1 (10 days after the intervention), M3 (90 days after the intervention) and M6 (180 days after the intervention)] the *status* of Coronavirus infection will be monitored by real-time PCR, in the case of symptomatic, and coronavirus serology every 3 months after vaccination with BCG or placebo (chart below). The tests will be performed with the purpose of having the diagnosis of the infection either through the real-time polymerase chain reaction (RT-PCR) technique and/or through the qualitative identification of IgM+IgA and/or IgG antibodies in the detection of infections that occurred asymptotically and that may have been attenuated by the intervention with the BCG vaccine. For individuals receiving specific immunization against SARS CoV 2, serology will not be used for diagnosis of asymptomatic infection.

At the time of recruitment hiv serology and BHCG dosage will also be collected for *women with status* in order to meet the eligibility criteria. The time between the examinations collected in the recruitment and the effective inclusion in the study should be up to 10 calendar days. If the return occurs between the third and tenth day, and the

participant presents symptoms compatible with COVID-19 upon return, the participant should recollect the RT-PCR.

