Participants who present some test results collected during the study outside the normal range will be evaluated by the study physician. It should be indicated in the participant's folder that this result has been verified and whether or not there is clinical significance. If any, the participant should be referred for specialist evaluation at the hospital where his follow-up is being carried out.

Visits	Evaluations	Exams	Procedures
Screening or Recruitment	Face-to-face assessment of eligibility criteria, application of the TCLE	NASOarchyeal swab RT-PCR, anti-SARS-Cov-2 antibody levels, BHCG dosage and HIV serology	Invitation to participate in the study, application of the TCLE, collection of clinical samples (nasopharangeal swab and blood).
Inclusion or M0 0 day of preventive treatment (ToT) (BCG or placebo)	Face-to-face assessment with confirmation of eligibility, clinical inclusion visit, collection of exams and dose of BCG or placebo	IGRA; Complete blood count, lipidogram, albumin, HbGlic, LDH, PCR, ESR, D-D-Dmer; and biomarkers*.	Nursing and medical consultation. Collection of clinical sample (blood). Application of preventive treatment.
S1 - S12 7-90 days of preventive TTO (±3 days)	Telephone and/or SMS contact, and/or weekly email and sending photo of the injection site	No exams	Fever questionnaires and/or respiratory signs and symptoms and photo submission of the injection site
M1 10 days of preventive TTO (±5 days)	Face-to-face visit to the laboratory for blood collection for biomarkers	Anti-Anti-SARS-Cov-2 antibody levels; Complete blood count, lipidogram, albumin, HbGlic, LDH, PCR, ESR, D-D-Dmer; and biomarkers*.	Collection of clinical sample (blood).
M3 90 days of preventive TTO (±14 days)	Face-to-face clinical visit for follow-up and blood collection for serology	Anti-Anti-SARS-Cov-2 antibody levels	Nursing and/or medical consultation. Collection of clinical sample (blood).
M4/M5 120/150 days of preventive Tom (±14 days)	Telephone contact and/or SMS, and/or weekly email	No exams	Fever questionnaires and/or respiratory signs and symptoms
M6 180 days of preventive TTO (±14 days)	Face-to-face clinical visit to close the study and for blood collection for serology	Anti-Antibody levels anti-SARS-Cov-2.	Nursing consultation. Collection of clinical sample (blood).
Fever and/or respiratory signs and symptoms	Face-to-face visit to the Worker's Health sector of its study center to collect exams	RT-PCR	Clinical sample collection (swab and blood).

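### The primary infection analysis is timed at 30 days as well as 6 months without saying whether 30 days is an endpoint or a data cut; neither reading supports a primary claim on infection

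*Combined protocol and SAP*

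**What the plan says.** **Timing.** The Statistical Analysis Plan section names cumulative incidence of SARS-CoV-2 infection and of severe COVID-19 as the primary efficacy comparisons and continues: "These analyses will occur when the last enrolled research subject has completed 30 days and 6 months of preventive treatment". The inputs are diagnostic test results "as well as the data available in participating hospitals and national electronic notification systems of COVID-19". Nothing ranks the two times or gives a separate case definition for 30 days.

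**Horizon elsewhere.** The Goals section sets a 6-month period. Under Primary Outcome 1, the sample size assumes a control-group "accumulated incidence of SARS-CoV-2 infection of 30% after 6 months of follow-up". No 30-day rate or power is stated.

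**Detection.** Under Study visits, RT-PCR is done in symptomatic participants, and serology is there to find infections without symptoms. The post-dose visits are "M1 (10 days after the intervention), M3 (90 days after the intervention) and M6 (180 days after the intervention" days. The visit table adds the windows: "M1 10 days of preventive TTO (±5 days"), "M3 90 days of preventive TTO (±14 days") and "M6 180 days of preventive TTO (±14 days"). Symptom contacts are weekly until M3. A participant with symptoms also has a visit with serology 14 to 30 days after onset.

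**COVID-19-vaccinated participants.** The closing paragraphs of the objectives name M3 and M6 as the visits for detecting asymptomatic seroconversion. They drop serology for anyone given a specific COVID-19 vaccine, for whom a case needs symptoms plus RT-PCR. The Sample size section expects 80% of the cohort to be vaccinated.

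**Interim looks.** The Interim Analysis Plan allows one intermediate efficacy analysis, with a Z value of 2.78.

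**The concern.** A primary analysis needs one defined time point and a case definition that can be applied at that time. The 30-day wording can be read in two ways, and each has its own problem.

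If day 30 is an endpoint, the asymptomatic part of infection cannot be dated to it. The 30-day quantity would then differ in content from the 6-month quantity while carrying the same name and the same primary status. It would also rest on few events.

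If 30 days is a calendar cut (the date on which the last participant enrolled reaches day 30), participants enter the analysis with very different follow-up and different numbers of serology samples. The SAP specifies logistic or robust Poisson models and mentions neither an offset nor censoring. The cut would also be a further efficacy look with no allocation of type I error.

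Either way, a low-powered 30-day result could be reported as a primary finding on infection.

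**Working it through.** **1. Serology windows (visit table)**

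| Visit | Nominal day and window | Days |
|---|---|---|
| M1 | 10 ± 5 | 5–15 |
| M3 | 90 ± 14 | 76–104 |
| M6 | 180 ± 14 | 166–194 |

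Between M1 and M3 the gap is 76 − 15 = 61 days, and day 30 lies in no window. The centre-by-centre laboratory table adds nothing near day 30. Event-triggered serology for symptom onset on days 1 to 30 falls on days 1 + 14 = 15 to 30 + 30 = 60, but only symptomatic participants have it.

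**2. Who is affected.** With 80% COVID-19-vaccinated, 0.20 × 376 ≈ 75 per arm remain eligible for serological diagnosis. For the other 0.80 × 376 ≈ 301, symptoms plus RT-PCR is the whole definition.

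**3. Dating an M3 seroconversion.** Suppose the M1 sample is negative, the M3 sample is positive, and risk is constant and small. The chance that infection came before day 30 is (30 − 10)/(90 − 10) = 25%. At the window limits it runs from (30 − 15)/(104 − 15) = 17% to (30 − 5)/(76 − 5) = 35%.

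**4. The plan's own figures.** The expected counts in Primary Outcome 3 reproduce:
- Control: 0.2 × 376 × 0.30 = 22.6 and 0.8 × 376 × 0.15 = 45.1, stated as 23 + 45 = 68.
- BCG: 0.2 × 376 × 0.20 = 15.0 and 0.8 × 376 × 0.15 × 0.85 = 38.4, stated as 15 + 38 = 53.

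The stated 376 per arm does not follow from the stated inputs alone. For 30% versus 20%, two-sided 5% and 80% power, a two-proportion formula gives 294 (313 with continuity correction), and 376 gives 88.8% power. That is a separate matter and does not affect this point.

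**5. Events by day 30.** Constant hazard is assumed: risk at 30 days = 1 − (1 − p)^(30/180).

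| 6-month assumption | Control by day 30 | BCG by day 30 | Power at 376 per arm |
|---|---|---|---|
| 30% vs 20% | 1 − 0.70^(1/6) = 5.8%, 21.7 cases | 1 − 0.80^(1/6) = 3.7%, 13.7 cases | 28% |
| 68/376 vs 53/376 | 1 − (308/376)^(1/6) = 3.3%, 12.3 cases | 1 − (323/376)^(1/6) = 2.5%, 9.4 cases | 9% |

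Power is for a two-sided 5% test of two proportions.

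**6. Number undatable.** The share of controls infected between days 10 and 30 is 0.70^(10/180) − 0.70^(30/180) = 0.9804 − 0.9423 = 3.8%. Among 75 unvaccinated controls that is about 2.9 infections. The asymptomatic share is not in the documents; assuming 10% to 50%, about 0.3 to 1.4 control cases are undatable, against about 12 control cases by day 30. If nobody were COVID-19-vaccinated, it would be 0.038 × 376 = 14.3 infections, of which 1.4 to 7.2 are undatable, against about 22.

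**7. Data-cut reading.** The Schedule gives recruitment from 30/10/2020 to 31/12/2021, which is 427 days. With even recruitment (assumed), at the time the last participant reaches day 30:
- Not yet at day 90: (90 − 30)/427 = 14.1%, or 106 of 752.
- Not yet at day 180: (180 − 30)/427 = 35.1%, or 264 of 752.

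The Intervention section also mentions 4 months of recruitment. Taken as 120 days, the figures would be 60/120 = 50% and, since 150 exceeds 120, everyone.

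**The case against.** A reader might infer that 30-day incidence of infection cannot be derived at all, or that a 30-day result would be uninterpretable. The documents do not support that. Only routine serology is missing between days 15 and 76. Weekly contacts, symptom-triggered RT-PCR, and hospital and notification data make symptomatic confirmed infection and severe COVID-19 measurable by day 30. For the 80% expected to be COVID-19-vaccinated, the plan's definition can be applied at day 30 exactly as written. On the plan's figures the undatable control cases number about one or fewer. These objections stand and limit the point.

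The SAP sentence says when analyses will occur, which reads naturally as a pair of analysis dates, and the rest of the plan speaks only of 6 months. That is a fair reading, but the text does not settle it, and the data-cut reading brings unequal follow-up and an unplanned look.

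A reader might also infer that unequal follow-up biases the comparison of arms. It need not: allocation is 1:1, clinical staff are blinded, and follow-up should be similar in both arms. What suffers is the meaning of the estimated risk, which belongs to no fixed time.

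Finally, one might suppose that M1 seroconversions merely reflect infection around dosing. That depends on antibody kinetics the documents do not give, and the plan names only M3 and M6 for asymptomatic seroconversion.

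**Conclusion.** The point holds in limited form. The SAP gives 30 days the same primary standing as 6 months without defining it, and the goals and sample size support 6 months only.

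- As an endpoint, the weakness in ascertainment is real but small: it is confined to asymptomatic infections after M1 in the roughly 20% without a COVID-19 vaccine. Low power is the larger problem, about 28% under 30% versus 20% and about 9% under the plan's mixed-cohort counts.
- As a data cut, about 14% of participants would lack M3 and 35% would lack M6, and the analysis is an efficacy look outside the single planned interim.

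The event counts and power rest on constant risk over 6 months. The 14% and 35% rest on even recruitment over 427 days and would be larger with faster recruitment. The gap from day 15 to day 76 comes straight from the visit table.

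**What to change.** In the Statistical Analysis Plan section:

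1. Make 6 months the only primary time for SARS-CoV-2 infection and keep the plan's existing case definition. For all participants, that means symptomatic RT-PCR-confirmed infection and hospital and notification data to day 180. M3 and M6 seroconversion is added only for participants not COVID-19-vaccinated, as the objectives already require.
2. Label any 30-day analysis as secondary. Restrict it to symptomatic RT-PCR-confirmed COVID-19 with onset by each participant's own day 30, report severe COVID-19 by day 30 alongside, and count no serology-only cases.

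Fixing the 30-day analysis to each participant's own day 30 removes the ambiguity and the unequal follow-up. The change is to wording only and needs no new samples or visits. The sponsor gives up a 30-day primary claim on infection, which the plan was not sized to support.
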